11 PROTOCOL VIOLATIONS

A protocol violation occurs when the subject, investigator, or Sponsor fails to adhere to significant protocol requirements affecting the inclusion, exclusion, subject safety and primary endpoint criteria. Protocol violations for this study include, but are not limited to, the following:

Failure to meet inclusion/exclusion criteria

Use of a prohibited concomitant medication

Failure to comply with Good Clinical Practice (GCP) guidelines will also result in a protocol violation. The CPHS will determine if a protocol violation will result in withdrawal of a subject.

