BACKGROUND/ RATIONALE	Zilretta is approved for intra-articular injection into the knee joint for treatment of osteoarthritis (1). There are ongoing studies for intra-articular injection into the other large joints including the shoulder and hip joints (2). To our knowledge, there has been no prior study to prove efficacy of injection of the extended release steroid into the bursa. The bursae surrounding the hip joint including the iliopsoas and the greater trochanteric bursa are some of the larger bursae in the body. Conventional treatment for inflammation of these bursae is injection of corticosteroids (3). We believe that a long acting corticosteroid, if efficacious, can have a great impact. There is a significant population of patients suffering from chronic bursal pain, who might benefit. At our institute, bursal injection of the steroid in the region of hips is one of the most common locations, second to joint injections. To our understanding, the bursa surrounding the hip are deep enough to avoid side effects associated with subcutaneous injection of steroid. The current proposal is a pilot study.
STUDY DESIGN	This is a prospective, open-label, pilot study, to assess the safety and efficacy of FX006 (triamcinolone acetonide extended release injectable suspension 32 mg) , administered to patients with greater trochanteric bursitis.
PRIMARY OBJECTIVE	The primary objective will be to determine the safety and efficacy of this drug in bursal injections by monitoring the improvement in the pain from baseline, as established using the using a Numeric Pain Rating Scale (NPRS) score at the end of 12 weeks.
SECONDARY OBJECTIVES	Secondary objective is to determine any alteration in the Patient Global Impression of Change (PGIC) measure. This is used as an indicator to assess the patient's impression to change in treatments, to their chronic pain.
PRIMARY END POINT	The primary endpoint will be the improvement in the pain from baseline, at the end of week 12, as determined by the NPRS pain score
SECONDARY END POINT	The secondary endpoint will be any alteration in the PGIC measure, at the end of week 12.

NUMBER OF SUBJECTS

24 patients

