1 BACKGROUND/RATIONALE

Zilretta is approved for intra-articular injection into the knee joint for treatment of osteoarthritis (1). There are ongoing studies for intra-articular injection into the other large joints including the shoulder and hip joints (2). To our knowledge there has been no prior study to prove efficacy of injection of the extended release steroid into the bursa. The bursae surrounding the hip joint including the iliopsoas and the greater trochanteric bursa are some of the larger bursae in the body. Conventional treatment for inflammation of these bursae is injection of corticosteroids (3). We believe that a long acting corticosteroid, if efficacious, can have a great impact. There is a significant population of patients suffering from chronic bursal pain, who might benefit. At our institution, bursal injection of the steroid in the region of hips is one of the most common locations, second only to joint injections. To our understanding, the bursa surrounding the hip are deep enough to avoid side effects associated with subcutaneous injection of steroid. The current proposal is a pilot study.

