10 DISCONTINUATION AND REPLACEMENT OF SUBJECTS

10.1 Early Discontinuation of Study Drug

A subject may be discontinued from study treatment at any time if the subject, the investigator, or Flexion Therapeutics, Inc. feels that it is not in the subject's best interest to continue. The following is a list of possible reasons for study treatment discontinuation:

Subject withdrawal of consent (or assent)

Subject is not compliant with study procedures

Adverse event that in the opinion of the investigator would be in the best interest of the subject to

discontinue study treatment

Protocol violation requiring discontinuation of study treatment

Lost to follow-up

Flexion Therapeutics, Inc. request for early termination of study

If a subject is withdrawn from treatment due to an adverse event, the subject will be followed and treated by the Investigator until the abnormal parameter or symptom has resolved or stabilized.

All subjects are free to withdraw from participation at any time, for any reason, specified or unspecified, and without prejudice.

Reasonable attempts will be made by the investigator to provide a reason for subject withdrawals. The reason for the subject's withdrawal from the study will be specified in the subject's source documents. Refer to Section 10 for early termination procedures.

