10.3 Replacement of Subjects

Subjects who withdraw from the study treatment will be replaced.

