12 STATISTICAL METHODS AND CONSIDERATIONS

Sample size justification:

We plan to enroll 24 patients for the pilot study. This sample size is determined by the projected availability of eligible patients within the proposed study period (6 months). This pilot study will help to establish the safety and efficacy of the investigated treatment FX006, and the data collected in this study will allow us to plan a future efficacy trial.

Statistical analysis plan:

Descriptive statistics will be reported for demographics and all clinical variables collected in this study.

For the efficacy evaluated by NPRS and PGIC, we will use appropriate summary statistics (e.g. mean + standard deviation for variables with normal distribution or median and interquartile range for variables with skewed distribution) to report NPRS and PGIC at each time point and analyze their changes over time. For safety evaluated, we will report the frequency and percentage of patients who have received any treatment to emergent adverse events within 12 weeks.

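### A patient given a corticosteroid after FX006 can be withdrawn and replaced, and Section 12 has no rule for such patients, so the week-12 NPRS improvement may be overstated

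*Combined protocol and SAP*

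**What the plan says.** The relevant text is spread over several sections of the combined protocol and SAP.

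- **Section 1** names corticosteroid injection as the usual treatment for inflamed hip bursae. It is therefore a foreseeable next step for a patient whose pain persists or returns.
- **Section 6.2** opens by banning corticosteroids while the study runs, but each item in its list carries a window counted relative to screening. **Section 5.2**, criterion 9, requires patients to be willing to avoid restricted medications throughout the study.
- **Section 11** lists "Use of a prohibited concomitant medication" among the violations and adds: "The CPHS will determine if a protocol violation will result in withdrawal of a subject".
- **Section 10.1** gives, among possible reasons for stopping, "Protocol violation requiring discontinuation of study treatment". For what to do then, it says "Refer to Section 10 for early termination procedures".
- **Section 10.3** states: "Subjects who withdraw from the study treatment will be replaced".
- **Section 12** plans descriptive summaries of NPRS and PGIC at each time point. **Section 12.1** defines a safety population only. Neither mentions an efficacy set, missing scores, steroid use after the injection, or withdrawn and replaced patients.

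The synopsis describes the design: "This is a prospective, open-label, pilot study, to assess the safety and efficacy of FX006". It lists no control product.

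**The concern.** The event that can lead to withdrawal may depend on the outcome. A patient doing well has little reason to seek another corticosteroid for the hip; a patient doing badly has every reason. If the second kind of patient can be withdrawn and a new patient enrolled in the same place, the patients with a week-12 score may be weighted towards those in whom FX006 worked.

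Keeping the patient does not remove the problem. The week-12 NPRS then reflects FX006 plus a later corticosteroid, and the plan does not say whether that score counts as an FX006 result.

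In a single-arm study no comparator would expose either effect. Section 12 says the study will help to establish efficacy and will be used to plan a later efficacy trial, so an inflated improvement could carry into that trial's assumptions.

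**Working it through.** **Step 1: the path, link by link.**

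1. *Corticosteroid after injection is prohibited.* Supported by the opening of 6.2 and by inclusion criterion 9. Weakened by the screening-based windows in 6.2, which leave its reach after the injection unclear.
2. *Prohibited use is a violation.* Stated in Section 11.
3. *A violation leads to withdrawal.* Possible but not automatic. The CPHS decides, and no criterion for that decision is given.
4. *A withdrawn patient is replaced.* Section 10.3 speaks of withdrawal from study treatment. Sections 7.2.1 and 7.2.3 give one injection per subject, so after Day 1 no treatment remains to stop. The list in 10.1 mixes in loss to follow-up and withdrawn consent, which suggests that leaving the study is meant, but 10.3 does not say so.

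**Step 2: what a withdrawn patient contributes.** Section 8.1.6 collects NPRS and PGIC at each follow-up call. Section 8.1.1 records concomitant medication at study discontinuation as well, but no section asks for NPRS or PGIC at that point. The pointer in 10.1 to Section 10 is circular, because Section 10 contains no early-termination procedure. Section 10.1 requires follow-up only after withdrawal for an adverse event. A patient withdrawn before week 12 therefore has scores at the calls already made, but no planned value for the primary endpoint.

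**Step 3: size, on assumed inputs.** There is no plan figure to reproduce. The 24 comes from expected availability over six months, and the documents give no effect, SD, dropout rate or rate of steroid use. Assume that:

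- 24 patients complete;
- a fraction d of those injected is withdrawn and replaced, with d from 10% to 30%;
- g is the mean improvement of those kept minus that of those withdrawn, from 1 to 4 NPRS points.

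Injected n = 24/(1 − d), rounded up. Replaced k = n − 24. Completers-only mean minus all-injected mean = (k/n) × g.

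| d | 24/(1 − d) | n | k | g = 1 | g = 4 |
|---|---|---|---|---|---|
| 10% | 26.7 | 27 | 3 | 3/27 × 1 = 0.11 | 3/27 × 4 = 0.44 |
| 20% | 30.0 | 30 | 6 | 6/30 × 1 = 0.20 | 6/30 × 4 = 0.80 |
| 30% | 34.3 | 35 | 11 | 11/35 × 1 = 0.31 | 11/35 × 4 = 1.26 |

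**Step 4: does replacement drive the result?** Suppose 24 are injected, k have no week-12 score, and nobody is replaced. The difference is (k/24) × g. For k = 2 it is 0.08 to 0.33; for k = 5, 0.21 to 0.83; for k = 7, 0.29 to 1.17. The size is similar. What replacement adds is concealment: the report can show 24 week-12 scores with no visible gap.

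**Step 5: limits.** If k = 0 or g = 0, the difference is zero. If withdrawn patients had improved more than those kept, the sign would reverse. The second branch, where the patient is kept and treated again, cannot be sized, because the documents say nothing about the effect of a further steroid.

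**The case against.** The strongest reply is that the plan contains no rule that selects responders. Section 11 does not name corticosteroid use after the injection, withdrawal is left to the CPHS, and 10.1 lists only possible reasons. Section 10.3 may not apply once the single injection has been given. Nothing drops a violator's scores, stops the calls after a violation or restricts the week-12 summary to completers. Scores before withdrawal would still be reported at their time points.

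All of that stands, and it limits the claim. A reader might infer that patients in whom FX006 fails do drop out of the week-12 NPRS and that the improvement is overstated as a matter of course. The documents do not support that: they permit the path without prescribing it, and on the analysis they are silent. A reader might also take the illustrative figures as an estimate. They are not one, because both the withdrawn fraction and the gap are assumed.

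The reply does not remove the gap in Section 12. Because the CPHS decision has no stated criterion, membership of the primary result can turn on something that happens after injection and may be linked to outcome. Reading 6.2 as purely about the period before screening would leave its opening words without effect and sit badly with criterion 9. Earlier scores do not supply a week-12 value, which is the primary endpoint.

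**Conclusion.** The point holds in conditional form. Sections 6.2, 10.1, 10.3 and 11 together allow a patient treated with a corticosteroid after FX006 to be classed as a violator, withdrawn at the CPHS's discretion and replaced, and Section 12 does not keep that patient in the efficacy result. The root gap is the missing rule in Section 12; the list in Section 11 is only where the path starts.

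If steroid use follows poor response and the summary covers completers only, the week-12 improvement is overstated by about 0.1 to 1.3 NPRS points over the assumed ranges (27 to 35 injected for 24 completers). Whether any bias arises depends on how often patients are withdrawn and how much less they improved, and neither is known. This is a cheap improvement worth making before the data are summarised. It is not proof that the result will be wrong.

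**What to change.** In Section 12:

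- Define the efficacy set as all injected patients, including any who are withdrawn or replaced.
- Report the numbers injected, withdrawn and replaced, with reasons, and the number given a corticosteroid before week 12. Section 8.1.1 already captures the indication and dates of each medication.
- Present the observed week-12 NPRS summary beside one that assigns zero change from baseline to patients given a corticosteroid for hip pain before week 12. Zero change is one convention among several; naming it gives a number that a mean or median can use. State how any other missing week-12 score is handled.

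In Sections 10 and 11:

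- Continue the scheduled NPRS and PGIC calls through week 12 after a prohibited-medication violation for anyone who has not withdrawn consent.
- Take a last-contact NPRS and PGIC from anyone who leaves, and put this in place of the circular pointer in 10.1.

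The CPHS's withdrawal decision stays as it is. Separately, the sponsor must reconcile the opening of 6.2 with its screening-based windows, and the reference to study treatment in 10.3 with the single-injection design.

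The cost is a few sentences, the calls already scheduled, and a last-contact score for those who leave. No extra patients or visits are needed. The downside is that the reported improvement may be less favourable.

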12 STATISTICAL METHODS AND CONSIDERATIONS

Sample size justification:

We plan to enroll 24 patients for the pilot study. This sample size is determined by the projected availability of eligible patients within the proposed study period (6 months). This pilot study will help to establish the safety and efficacy of the investigated treatment FX006, and the data collected in this study will allow us to plan a future efficacy trial.

Statistical analysis plan:

Descriptive statistics will be reported for demographics and all clinical variables collected in this study.

For the efficacy evaluated by NPRS and PGIC, we will use appropriate summary statistics (e.g. mean + standard deviation for variables with normal distribution or median and interquartile range for variables with skewed distribution) to report NPRS and PGIC at each time point and analyze their changes over time. For safety evaluated, we will report the frequency and percentage of patients who have received any treatment to emergent adverse events within 12 weeks.

12.1 Data Sets Analyzed

All eligible patients who are randomized into the study and receive at least one dose of the study drug (the Safety Population) will be included in the safety analysis.

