3. STUDY DESIGN

3.1 Study Overview

This is a consented, pilot study in patients with pain and bursitis involving the greater trochanteric bursa, with administration of 32 mg FX006. The study will be conducted in male and female patients 18 years of age or older with symptomatic greater trochanteric bursitis. Each patient will be screened for eligibility with an ultrasound to confirm the diagnosis of bursitis, in the absence of prior MRI imaging done in the preceding three months. Based on the inclusion/exclusion requirements, they will be offered participation in the study to receive an intra-bursal injection of 32 mg FX006. Eligible and participating patients will receive treatment under ultrasound image guidance to the greater trochanteric bursa. Patients will be followed up by phone at 1, 2, 4, 8, and 12 weeks and mean NPRS pain scores and PGIC scores will be recorded. Adverse events, if any, will be reported immediately to the primary physician and any subsequent follow-up will be reported. The study will be completed in week 12 and all recorded patients' NPRS, PGIC and emergent findings, if any will be compiled into a HIPAA compliant database.

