5 SUBJECT SELECTION

5.1 Study Population

Subjects with a diagnosis of bursitis of greater trochanter, who meet the inclusion and exclusion criteria will be eligible for participation in this study.

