5.2 Inclusion Criteria

1. Written consent to participate in the study
2. Male or female greater than or equal to 18 years of age
3. Symptoms consistent with bursitis of greater trochanter for greater than or equal to 3 months prior to Screening (patient reported is acceptable)
4. Pain in hip for greater than 15 days over the last month (as reported by the patient)
5. Hip bursitis as determined by clinical examination and clinical features. Where Magnetic Resonance Imaging (MRI) data is available, it will be used to confirm the bursitis diagnosis. Also, pain relief in subjects that have been treated with bursal injections containing an

anesthetic (such as ropivacaine) is in itself indicative of bursitis

6. Body mass index (BMI) less than or equal to 40 kg/m²
7. Ambulatory and in good general health
8. Willing and able to comply with the study procedures and visit schedules and able to follow verbal and written instructions.
9. Willing to abstain from use of protocol-restricted medications during the study

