7.1 Treatment Plan

The patient will make a one-time visit to the outpatient radiology department at Memorial Hermann Hospital at the Texas Medical Center, and will be expected to stay for a maximum of 2 hours. Each patient will be consented for the procedure and a baseline assessment using the NPRS and PGIC measures will be made.

24 patients will be injected with the 5ml of FX006. This injection may be followed with up to 3ml of ropivacaine (depending on the capacity of the bursa), under ultrasound guidance. The data collected from the patient and subsequent follow-up will be maintained by the clinical team throughout the 12 weeks of the subject participation.

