16 APPENDIX 1: SCHEDULE OF STUDY ASSESSMENTS

	VISIT 1 (Day 1)	VISIT 2 (Week 2)	VISIT 3 (Week 4)	VISIT 4 (Week 8)	VISIT 5 (Week 12)
Informed Consent	X				
Medical History	X				
Abbreviated Physical Exam	X				
Height	X				
Weight	X				
Vital Signs	X				
Pregnancy Test (Urine)	X				
Dispensing or Administration of Study Drug	X				
Initiate Subject Diary	X				
Subject Diary Review		X	X	X	X
Concomitant Medication Review	X	X	X	X	X
Adverse Events	X	X	X	X	X

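### Section 12.1 limits the Safety Population to eligible, randomized patients in a single-arm trial, so an injected patient later found ineligible could be left out of the safety analysis

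*Combined protocol and SAP*

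**What the plan says.** Section 12.1 (Data Sets Analyzed) bases the safety analysis on "All eligible patients who are randomized into the study and receive at least one dose of the study drug (the Safety Population". It is the only analysis set defined anywhere in the combined protocol and SAP. Three conditions are joined: eligible, randomized and dosed.

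The design has one arm. The synopsis describes an open-label pilot and lists the control product as not applicable, and section 7.1 has all 24 patients injected with FX006.

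*Eligible* is used in two ways:

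- Section 5.1 refers to subjects with the diagnosis "who meet the inclusion and exclusion criteria will be eligible for participation in this study".
- Section 3.1 uses the word for the decision made before treatment: "Eligible and participating patients will receive treatment under ultrasound image guidance to the greater trochanteric bursa".

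Section 11 lists "Failure to meet inclusion/exclusion criteria" among its protocol violations and adds: "The CPHS will determine if a protocol violation will result in withdrawal of a subject". Section 10.3 provides for replacing subjects who withdraw from study treatment. Section 12 promises a frequency and percentage for adverse events over 12 weeks, but states no clear denominator.

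**The concern.** A safety set normally follows exposure: whoever received the drug is counted. Here two further conditions stand in front of exposure. One of them, randomization, cannot be met by anyone. An analyst must therefore set part of the sentence aside, and has no guidance on whether *eligible* still binds.

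If it does, an exposed patient can leave the denominator, and any event that patient had can leave the numerator, because of a criterion found afterwards to have failed. Section 2.1 makes safety part of the primary objective and asks about any adverse event within 12 weeks of injection. It sets no eligibility condition.

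The visit structure makes this more than a formality. Section 7.1 says: "The patient will make a one-time visit to the outpatient radiology department". In Appendix 1 the physical exam, the urine pregnancy test and the row "Dispensing or Administration of Study Drug" are all marked at Visit 1, and section 7.2.1 gives the drug once per subject. A failed criterion that surfaces later therefore concerns someone whose exposure is complete. Two analysts working from the same text could report different percentages, and the choice could be made after the events are known.

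**Working it through.** The plan gives no figure to reproduce. The sample size of 24 rests on feasibility (section 12), with no power, alpha or safety threshold. The check has two parts.

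**1. Does any other section settle the reading?**

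| Section | What it covers | Does it fix the safety denominator? |
|---|---|---|
| 2.1 | Objective: any adverse events within 12 weeks of injection | No, but it conflicts with excluding an injected patient |
| 3.1 | *Eligible* as a screening decision | On this reading every injected patient is in |
| 5.1 | *Eligible* as meeting the criteria | On this reading a patient who failed them can be out |
| 9.1 | Adverse-event collection from administration, no eligibility condition | No; data capture |
| 9.3, 13.1 | Serious-event reporting and source records for all treated patients | No; data capture |
| 10.3 | Replacement after withdrawal from treatment | No; silent on analysis of the replaced subject |
| 11 | Failed criteria foreseen; withdrawal left to the CPHS | No; silent on analysis |
| 12 | Frequency and percentage over 12 weeks | No; denominator not clearly stated |

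Nothing chooses between the two readings. If *randomized* is applied literally, the set contains 0 of the 24 patients.

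**2. How far can the reported percentage move?**

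Inputs: n = 24 dosed (sections 7.1 and 12). Let x be the number of patients with an adverse event. The number left out, k, is not in the documents; k = 1 and k = 2 are assumed for illustration.

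One patient left out, who had an event:

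(x − 1)/23 − x/24 = (x − 24)/552

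The largest fall is at x = 1: −23/552 = −4.2 points, that is, 1/24 = 4.2% becomes 0/23 = 0%.

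One patient left out, who had no event:

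x/23 − x/24 = x/552

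The largest rise is at x = 23: 23/552 = +4.2 points. With few events it is small. At x = 1 it is 1/552 = +0.2 points (4.2% becomes 4.3%).

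Two patients left out:

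- Both had events, x = 2: 0/22 − 2/24 = −8.3 points.
- Neither had an event, x = 22: 22/22 − 22/24 = +8.3 points.

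In general the largest shift either way is k/24.

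Exact (Clopper-Pearson) 95% intervals for the worst downward case:

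- 1/24: 0.1% to 21.1%
- 0/23: 0% to 14.8%, the upper limit being 1 − 0.025^(1/23)

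If there are no events at all, leaving out one patient moves the upper limit only from 14.25% (0/24) to 14.82% (0/23).

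**The case against.** The best defence is that section 12.1 simply follows the trial sequence of judged eligible, entered, then dosed, as section 3.1 does. Section 5.1 can also be read as describing an entry decision, and nothing provides for eligibility to be revoked after injection. Section 12.1 says who is included, with no instruction to remove violators. Section 12 also promises descriptive statistics for all clinical variables collected, and adverse events are collected for everyone treated. This makes the inclusive reading possible, but it does not exclude the other. On the inclusive reading *eligible* adds nothing to the dosing condition, since only patients judged eligible are injected. The sections on data capture do not define a denominator.

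Some of the defence stands. Patient-reported criteria are weak evidence that failures will be found later. For a criterion such as "Pain in hip for greater than 15 days over the last month (as reported by the patient", the report itself satisfies the wording. Undisclosed recent steroid use (section 5.3) is a more plausible route. So is disagreement within the plan: the look-back for prior intra-bursal corticosteroid is three months in section 5.3 and six in section 6.2, and these must be reconciled separately.

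It is also fair that the consequence is small. The analysis is descriptive with no decision rule, the upward limit needs 23 of 24 patients to have events, and the exact interval for 1/24 is wider than any of these shifts.

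**Conclusion.** The concern holds. The only analysis set in the plan is wrong as written. One of its conditions fits no patient, and another can be read to remove an exposed patient from an outcome that belongs to the primary objective. This should be fixed, although the numerical effect is limited: at most 4.2 percentage points for one patient left out and 8.3 for two, in either direction, and zero if no injected patient proves ineligible. These sizes assume exactly 24 dosed. The number left out is an assumption, because the documents give no rate of ineligible enrolment. Data collection and serious-event reporting are not at fault; they already cover every treated patient.

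**What to change.** Replace the definition in section 12.1 with:

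> Safety Population: all subjects who receive any amount of FX006, regardless of eligibility, protocol violation, withdrawal or replacement.

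Withdrawal and replacement are named because sections 10.3 and 11 leave the analysis status of those subjects unstated.

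As a separate editorial correction, the adverse-event sentence in section 12 and the synopsis is garbled, although sections 2.1, 4.3 and 9.1 make its meaning plain. It could read:

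> Number and percentage of subjects in the Safety Population with at least one treatment-emergent adverse event within 12 weeks of injection.

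The cost is one sentence in section 12.1 and one rewording in two places. No new data are needed. The reported rate differs from that under the present wording, read with *randomized* set aside, only if an injected patient is found ineligible. The change should be made before results are known, so that the denominator is not chosen with the events in view.
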